# ABBREVIATIONS/TERMINOLOGY

*Arthroplasty* is a surgical procedure to restore the integrity and function of a joint. A joint can be restored by resurfacing the bones; an artificial joint (prosthesis) may also be used. Osteoarthritis (OA) or degenerative joint disease is a loss of the cartilage or cushion in a joint, and is the most common reason for arthroplasty

COFAS - Canadian Orthopaedic Foot & Ankle Society

*Good Manufacturing Practice (GMP)* - regulations set forth by the United States Department of Health and Human Services by the Food and Drug Administration (FDA) under the regulations 21 CRF Parts 808, 812, 820.

ICH - The International Conference on Harmonization

*ICH E6*\_Good Clinical Practice (GCP)

*Good Clinical Practice (GCP)* is an international ethical and scientific quality standard for designing, conducting, recording, and reporting trials that involve human subjects. Compliance with GCP assures that the rights, safety, and well-being of trial subjects are protected and that the clinical trial data are credible. This International Conference on Harmonization (ICH) guidance provides a unified standard for the European Union, Japan, and the United States to facilitate the mutual acceptance of clinical data by the regulatory authorities in those jurisdictions.

*IRB/EC/REC*- is an Institutional Review Board, Ethical Review Committee, Research Ethical Committee - a committee established to review and approve research involving human subjects. The purpose of the IRB/EC/REC is to ensure that all human subject research be conducted in accordance with all federal, institutional, and ethical guidelines

**ISO 14155:2011** addresses good clinical practice for the design, conduct, recording and reporting of clinical investigations carried out in human subjects to assess the safety or performance of medical devices for regulatory purposes. The principles set forth in ISO 14155:2011 also apply to all other clinical investigations and should be followed as far as possible, depending on the nature of the clinical investigation and the requirements of national regulations.

**ISO 14155:2011** also specifies general requirements intended to protect the rights, safety and well-being of human subjects, ensure the scientific conduct of the clinical investigation and the credibility of the results, define the responsibilities of the sponsor and principal investigator, and assist sponsors, investigators, ethics committees, regulatory authorities and other bodies involved in the conformity assessment of medical devices.

Osteolysis - pathological destruction or disappearance of bone tissue.

Subsidence- sinking or settling in bone, as of a prosthetic component of a total joint implant.

Study Title	The INFINITY ™ Total Ankle Replacement Follow-up (ITAR)					
Study Design	Prospective, multi-site, multi-year post-market clinical follow-up study					
Study Group	Primary/Unilateral and/or bilateral Total Ankle Arthroplasty subjects implanted with INFINITY TM Total Ankle System					
N Subjects	200 with 10 sites					
Follow-Up Schedule	Subject enrollment will consist of a Pre-operative, Operative, 6 months, 1 yr., 2 yr., 5yr., 7 yr., 10 yr., and an unscheduled visit as needed.					
Primary Objective	Evaluate the long-term survivorship of the INFINITY ™ implant over 10 years					
Secondary Objective(s)	
 
Secondary objectives assessed will be to:
 
Identify and assess the implant for component loosening and/or subsidence, any osteolysis and/or cyst formation through radiographic evaluation early and throughout the lifetime of the implant.
 
Compare the improvements in self-reported physical, mental, and social health measures from pre-op through 10 years post operatively; assessed by PROMIS® Global Health.
 
Compare pain and functional improvement in the Ankle Osteoarthritis Score (AOS), which is a visual analogue scale specifically designed as a modification of the Foot Function Index.
 
Compare the improvement in patient/physician reported function scores from pre-op through 10 years post-operatively, assessed by the FAOS questionnaire.
 
Compare satisfaction of total ankle replacement post operatively utilizing a four point scale
 
Identify and report the safety of the implant in terms of complications and adverse events.
 
					
Inclusion Criteria	
 
Subjects to be included in the study must meet all of the following criteria:
 
Be 21 years of age or older at the time of surgery;
 
Diagnosed with unilateral and/or bilateral ankle joint disease;
 
Diagnosed with ankle joint damage from rheumatoid arthritis, post-traumatic, or degenerative arthritis;
 
Willing and able to consent to participate (written, informed consent;
 
Willing and able to attend the requested follow-up visits;
 
A clinical decision has been made to use INFINITY™ Total Ankle System replacement prior to enrollment in the research.
 
					
Exclusion Criteria	
 
Subjects will be excluded from the study if they meet any of the following criteria:
 
Subjects with an ankle condition, as determined by the investigator, to be an inappropriate candidate for a total ankle replacement;
 
Subjects requiring revision total ankle replacement of the ankle being considered for study
 
					

# **PROTOCOL SYNOPSIS**

# **SCHEDULE of EVENTS**

Procedures	Pre-op	Op.	6 mo +/-30 days	1 yr +/-60 days	2 yr +/-60 days	5 yr +/-60 days	7 yr +/-60 days	10 yr +/-60 days	Study Close
Informed Consent	Х								
Inclusion/Exclusion Criteria	X								
Medical History/Demographics	X								
Operative (Surgical) procedure/device		X							
PROMIS Global Health	X		X	Х	X	X	Х	X	
Ankle Osteoarthritis Score (AOS)	X		X	X	X	X	X	X	
FAOS Questionnaire	X		X	X	X	X	X	X	
Total Ankle Replacement Satisfaction			X	X	X	X	X	X	
Radiographic Assessment (Investigator requirement)	X		X	X	X	X	X	Х	
Adverse Event Assessment			X	Х	Х	Х	Х	X	
End of Study									X
Surgical Intervention 									
*Sponsor-approved Unscheduled Visit 									

& These are not scheduled time point events but will be observed for throughout study participation.

# **INTRODUCTION**

Wright Medical introduced the INFINITYTM, total ankle system, for use in total ankle arthroplasty replacement (TAR) in the United States in 2013 and in Canada and Europe in 2014. The INFINITYTM Total Ankle System is a fixed-bearing, bone-sparing total ankle prosthesis that restores mobility to a failing ankle joint. It encompasses three components (i.e., tibial tray, tibial insert, and talar dome).

The INFINITYTM Total Ankle System is indicated in patients with ankle joints damaged by severe rheumatoid, post-traumatic, or degenerative arthritis, as well as for patients with a failed previous ankle surgery. Its intended use is to give patients limited mobility by reducing pain, restoring alignment and replacing the flexion and extension in the ankle joint.

The technological features of the INFINITYTM Total Ankle System are similar to the predicate devices (INBONE® Total Ankle System, DePuy AgilityTM, INBONE® II Total Ankle System), which have all been cleared through the 510K process with the FDA, with regard to design and materials. The goal of the design was to limit the amount of bone resection and soft tissue dissection required for ankle arthroplasty; hence the overall profile of the INFINITYTM Total Ankle System was significantly reduced along with the incision length required to perform the surgical procedure.

Currently, there has been little data published characterizing the use of the INFINITYTM Total Ankle System. This study's data collection will begin early in the utilization and implantation of the product and the data will allow for the filling of this gap in knowledge, support the long-term data collection, as well as the product's use and performance.

# **STUDY OVERVIEW**

#### Study Rationale

The primary outcome measure of this post-market clinical observational study is to collect data relating to the INFINITYTM Total Ankle System survivorship at 10 years. The secondary outcome measures are to characterize the improvements after implantation over a 10 year period using patient reported outcome measures related to quality of life, pain and functional improvements, safety of the implants, as well as radiographic assessments (X-Rays)

The outcome measures collected in this study will be analyzed and reported as required for local, regional, and country requirements (i.e., regulatory authorities and notified bodies).

## Part Numbers and Brief Descriptions of Configurations

All configurations and sizes listed in the table below can be included in the study. These products are manufactured according to ICH GCP in accordance with applicable Good Manufacturing Practice (GMP) and with the ISO 14155:2011: through relevant manufacturing and related validation processes.

Part No.	Description	Part No.	Description			
	INFINITY TM Poly Insert	INFINITY™ Tibial Component				
33651106	POLY INSERT, SZ1/1+ 6MM	33650001	Tibial tray SZ1 STD			
33651108	POLY INSERT, SZ1/1+ 8MM	33650002	Tibial tray SZ2 STD			
33651110	POLY INSERT, SZ1/1+ 10MM	33650003	Tibial tray SZ3 STD			
33651112	POLY INSERT, SZ1/1+ 12MM	33650004	Tibial tray SZ4 STD			
33652206	POLY INSERT, SZ2 6MM	33650005	Tibial tray SZ5 STD			
33652208	POLY INSERT, SZ2 8MM	33650013	Tibial tray SZ3 Long			
33652210	POLY INSERT, SZ2 10MM	33650014	Tibial tray SZ4 Long			
33652212	POLY INSERT, SZ2 12MM	33650015	Tibial tray SZ5 Long			
33653206	POLY INSERT, SZ2 +6MM	INFIN	NTY™ Talar Component			
33653208	POLY INSERT, SZ2 +8MM	33630021	Talar Dome SZ 1			
33653210	POLY INSERT, SZ2 +10MM	33630022	Talar Dome SZ 2			
33653212	POLY INSERT, SZ2 +12MM	33630023	Talar Dome SZ 3			
33653306	POLY INSERT, SZ3 6MM	33630024	Talar Dome SZ 4			
33653308	POLY INSERT, SZ3 8MM	33630025	Talar Dome SZ 5			
33653310	POLY INSERT, SZ3 10MM	INBO	NE® II Talar Component			
33653312	POLY INSERT, SZ3 12MM	220220901	Talar Dome SZ 1 SULCUS			
33654307	POLY INSERT, SZ3 + 7MM	220220902	Talar Dome SZ 2 SULCUS			
33654309	POLY INSERT, SZ3 + 9MM	220220903	Talar Dome SZ 3 SULCUS			
33654311	POLY INSERT, SZ3 11MM	220220904	Talar Dome SZ 4 SULCUS			
33654313	POLY INSERT, SZ3 13MM	220220905	Talar Dome SZ 5 SULCUS			
33654406	POLY INSERT, SZ4 6MM	IN	BONE® II Talar Stem			
33654408	POLY INSERT, SZ4 8MM	200347901	TALAR STEM 10MM			
33654410	POLY INSERT, SZ4 10MM	200347902	TALAR STEM 14MM			
33654412	POLY INSERT, SZ4 12MM					
33655407	POLY INSERT, SZ4 +7MM					
33655409	POLY INSERT, SZ4 +9MM					
33655411	POLY INSERT, SZ4 +11MM					
33655413	POLY INSERT, SZ4 +13MM					
33655506	POLY INSERT, SZ5 6MM					
33655508	POLY INSERT, SZ5 8MM					
33655510	POLY INSERT, SZ5 10MM					
33655512	POLY INSERT, SZ5 12MM					

*Indications for Use (IFU)* Indications for use in patients with ankle joints damaged by:

- Severe rheumatoid arthritis; ٠
- ٠ Post-traumatic, or;

- Degenerative arthritis;
- Additionally, for patients with a failed previous ankle surgery

## Risks and Benefits Benefits

The clinical benefit to the INFINITYTM Total Ankle System is to give a patient improvement in mobility by reducing pain, restoring alignment and replacing the flexion and extension in the ankle joint.

## Risks

There are no additional risks anticipated, specific to participating in this study. The study is not examining any experimental procedures and participation in the study is not predicted to affect the medical treatment received by enrolled subjects. The INFINITYTM Total Ankle does not pose additional risks compared to other standard total ankle systems when used for the same clinical application. The risks of ankle replacement include intra-operative complications such as peri-prosthetic fracture, neurovascular damage and tendon injury. Early post-operative problems include infection, wound healing problems, deep vein thrombosis, and peri-prosthetic fracture. Late complications include infection, peri-prosthetic fracture, loosening, implant failure, ongoing pain. These risks are comparable to those in alternative implants and alternative surgical procedures.

# **STUDY DESIGN**

The selected design is a multi-center, non-randomized, prospective study of 200 subjects in the US with ten investigational sites and a potential for more as needed to meet the enrollment requirements. The study subjects included are those with ankle joints damaged by severe rheumatoid arthritis, post-traumatic disease, and degenerative arthritis and implanted with the INFINITYTM Total Ankle System.

## Primary and Secondary Endpoints

The primary endpoint is a survivorship rate at 10 years as defined with a Kaplan Meier survivorship analysis. Secondary endpoints identify, assess and compare functional improvements or deviations collected through investigator observation and patient self-reporting, and include:

• Identification and assessment of the implant through radiographic assessment for component loosening and/or subsidence, any osteolysis and/or cyst formation early and throughout the lifetime of the implant.

- Comparison of improvements in self-reported physical, mental, and social health measures from pre-op through 10 years post operatively; assessed by PROMIS®.
- Comparison of pain and functional improvement from pre-op through 10 years in the AOS which is a visual analogue scale specifically designed as a modification of the Foot function Index.
- Comparison of the improvements in patient/physician reported function scores from pre-op through 10 years post-operatively, assessed by FAOS scores.
- Compare satisfaction of total ankle replacement post operatively utilizing a four point scale
- Identification and reporting on the safety of the implant in terms of complications and adverse events.

## Planned visits and Follow-Up Time Points

Subjects will be seen prospectively at the following intervals Pre-Op, Operative, 6 months, 1, 2, 5, 7, and 10 years. If there are special circumstances where the subjects require a visit outside the windows of the established visits, the investigator may seek approval from Wright Medical for an acceptance of an" unscheduled visit" and it will be determined if the data will be included and analyzed.

# SITE/SUBJECT SELECTION

Clinical Research Sites will be identified to participate in the study based on current experience, and training in the use of the INFINITYTM Total Ankle System and according to ICH GCP guidelines and ISO 14155: 2011 which states; qualified by education, training and experience to perform his or her respective task(s). It is the expectation the surgeon will adhere to and follow the INFINITYTM Surgical Technique and have knowledge of the contraindications as provided in the Instructions for Use (IFU). (See Appendix A).

## **Study Design Summary**

#### **Informed Consent**

Prior to any conducting any protocol required data collection, including evaluations and questionnaires, written informed consent must be obtained from the subject in compliance with 21 CFR Part 50.

Subjects will be recruited based on interest in participating in the study. All subjects will be consented by an appropriately trained clinician or research nurse using the IRB/EC/REC approved consent form in order to participate in the study and prior to any data collection, or any study procedure. The study clinician or research nurse will assess whether the patient can give informed consent or not during the consent process. The potential participant must be allowed ample time to review the informed consent and should be allowed to take the time to read, review, ask questions, and receive answers as well as being fully informed of all aspects of the study before a decision is made to participate. The source documentation will include a statement of the consent process and include details of the person taking consent for study participation.

#### Screening

Subjects with interest in participating in the study, after signing the informed consent document, will then be invited to participate if they meet the Inclusion Criteria.

#### **Point of Enrollment**

Subjects will be considered enrolled in the study when they have:

- Been informed of all aspects of the study and have signed Informed Consent document
- Acknowledged the appropriate patient data release information (included in the Informed Consent document)
- Satisfied the Inclusion/Exclusion Criteria
- Implanted with the Device

Investigators should document subject enrollment by completing the screening and enrollment logs located within the trial master file. The Source documentation should clearly state that all inclusion and exclusion criteria have been met and the patient data release and informed consent documents have been signed and appropriately dated prior to any study related activity,

The investigative sites will be assigned three digit a site code **\*\*\***, and at enrollment the subject will be assigned a sequential subject identification number corresponding to the order the subject was enrolled (i.e. the first subject enrolled at each site will be site number **\*\*\*** followed by subject identifier 001). The assigned codes will be used to identify the subject on all case report forms. All investigative sites will be provided protocol training of the during the site initiation visits. Investigative sites will be provided paper case report forms/booklets, which may be used as source documentation, these must signed by the individual completing the form; i.e., coordinator, patient, or investigator.

## Study Duration, Subject Participation and Estimated Enrollment Period

The total study duration from , first patient, first visit, (FPFV) to last patient, last visit (LPLV) is expected to be 12 years, with a recruitment period of 24 months The investigator/investigative site must make every reasonable attempt to contact the patients to complete all scheduled post-operative visits within the visit window. In instances where the individual cannot be reached, the investigator/investigative site will document at least two attempts to contact the patient via phone/mail and one certified letter for each time point. Due to the length of this study and the risk of lost to follow-up potential, if a subject has an inability to and, for some unforeseen reason cannot be seen on the hospital site, patient reported outcome measure case report forms may be completed remotely by post or telephone and returned to the investigative site/investigator for review and submission. If this process is applied it must documented and reported to Wright accordingly.

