## **Device** Failure

Subjects will be considered a treatment failure, and will be withdrawn from the study if any sections of the device (tibial or talar metal components) have been removed at any time during their participation. This should be reported onto the adverse event form. In addition, any surgical intervention during study participation that relates to their total ankle replacement will be reported on the surgical intervention case report form.

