### Survivorship of INFINITY® Total Ankle System

Survivorship of INFINITY® Total Ankle System will be based on secondary surgical intervention performed on the original implant. The Kaplan Meier survivorship method and life table analysis will be employed. Time to surgical intervention due to implant failure will be the survivorship endpoint of INFINITY® Total Ankle System. In addition, time to reoperation to exchange or remove any part of the INFINITY® Total Ankle System or surgical intervention due to failure of the implant as survivorship endpoint will also be analyzed. Subjects who did not undergo revision or reoperation due to implant failure at the time of reporting will be censored at the last follow-up. The Kaplan Meier survival curve with the 95% Confidence Interval will be constructed.

Year since	Number	Number of	Lost	Survival	95%
implantation	at start	failed implant		Rate	Confidence
					Interval
0-1	1		I		
1-2					
2-3					
3-4					
4-5					
5-6					
6-7					
7-8					
8-9					
9-10					

Table . Kaplan-Meier life-table survival of INFINITY® Total Ankle System.

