### 2. Report Timing of survivorship assessment

There will be two timepoints to assess and report survivorship, at the 5th (intermediate survivorship assessment) and 10th (long-term survivorship assessment) year follow-up.

At the intermediate assessment of survivorship (5th year follow-up), only patients with follow-up scores obtained at least four years after surgery will be included in the analysis. Patients who underwent reoperation or revision surgery with in four years of surgery will not be excluded. At the final assessment of survivorship (10th year follow-up), only patients with follow-up scores obtained at least eight years after surgery will be included in the analysis. Patients who underwent reoperation or revision surgery will be included in the analysis. Patients who underwent reoperation or revision surgery will be included in the analysis.

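### Remote follow-up specifies PROM forms but no revision enquiry, and the SAP does not require known implant status at censoring, so an unreported revision would count as event-free time.

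*Protocol*

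**What the plan says.** The protocol (Primary and Secondary Endpoints) states: "The primary endpoint is a survivorship rate at 10 years as defined with a Kaplan Meier survivorship analysis". The SAP (Survivorship of INFINITY® Total Ankle System) defines the event: "Time to surgical intervention due to implant failure will be the survivorship endpoint of INFINITY® Total Ankle System". A further analysis adds reoperation to exchange or remove any part of the system.

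Four provisions decide how a subject who stops attending is handled.

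- **Remote contact** (Protocol, Study Duration, Subject Participation and Estimated Enrollment Period). If a subject cannot be seen on site, "patient reported outcome measure case report forms may be completed remotely by post or telephone". The forms go back to the site for review and submission. No adverse event form, surgical intervention form or implant-status question is named for this route.
- **Reporting of surgery** (Protocol, Device Failure). "any surgical intervention during study participation that relates to their total ankle replacement will be reported on the surgical intervention case report form". The footnote to the Schedule of Events, in both documents, adds that such interventions are watched for throughout participation.
- **Entry to the analysis** (SAP, Report Timing of survivorship assessment). At year 10, "only patients with follow-up scores obtained at least eight years after surgery will be included in the analysis". At year 5, "only patients with follow-up scores obtained at least four years after surgery will be included in the analysis". Subjects who had a reoperation or revision are kept.
- **Censoring** (SAP, Survivorship section). "Subjects who did not undergo revision or reoperation due to implant failure at the time of reporting will be censored at the last follow-up".

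**The concern.** The primary endpoint needs two facts per subject: whether a qualifying operation has happened, and when. The only follow-up route written for the absent subject names neither. Yet a form collected by that route can serve as the late score that admits the subject, and its date can serve as the last follow-up.

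If a subject is revised at another hospital, the site does not learn of it, and a PROM form comes back at year 10, the implant is carried as event-free to year 10. Such an error can only raise survivorship. The planned output would not show it. The subject would not be counted as lost in the life table, and the accounting table (SAP, Patient Disposition and Accounting) counts subjects with complete data and with any data, not subjects with known implant status.

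**Working it through.** The plan has no figure to reproduce. The protocol says that the sample size was not calculated statistically, and neither document gives an expected survivorship, dropout rate or remote-contact rate. The check is in three steps.

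**Step 1: do the provisions connect?**

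- The instruments that the SAP treats as scores are PROMIS, FAOS and AOS. A late PROM form is therefore the natural reading of a follow-up score, though the term is undefined.
- Those three, as described, measure health, symptoms, pain and function. The satisfaction item concerns the ankle replacement but is described as rating satisfaction, not as recording surgery.
- The censoring rule refers to last follow-up, also undefined, and does not require that implant status was established then.

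The path from a posted form to event-free time is open on a natural reading, and nothing in either document closes it.

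**Step 2: illustrative size.**

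From the SAP: N = 155 enrolled. Assumed: true 10-year survival 90%; constant hazard; remote share r, remote from year 5 onward; share u of their later revisions unreported; no other censoring; remote status unrelated to revision risk.

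- Survival at year 5 = 0.90^(5/10) = 0.9487.
- Risk exposed to under-reporting = 0.9487 − 0.9000 = 0.0487.
- Missed events = 155 × r × u × 0.0487.
- Apparent 10-year survival = 0.90 + r × u × 0.0487.

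| r | u | Missed events | Apparent survival |
|---|---|---|---|
| 10% | 25% | 0.19 | 90.1% |
| 20% | 50% | 0.75 | 90.5% |
| 30% | 100% | 2.26 | 91.5% |

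The start of remote follow-up matters. With r = 30% and u = 100%, starting after year 2 gives 92.4% and after year 7 gives 90.9%. If true survival were 80%, the same extreme after year 5 gives 82.8%, a shift of 2.8 points.

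For scale, each missed revision is worth 1/155 = 0.65 points. The 95% half-width at 90% without censoring is 1.96 × √(0.90 × 0.10 / 155) = 4.7 points.

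**Step 3: does censoring at last confirmed status remove the bias?**

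Under the same assumptions, yes. Remote subjects leave the risk set at year 5, the hazard is estimated from subjects whose status is known, and the curve returns 90.0%.

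This works only if the late-score entry rule is also removed. Suppose PROM forms without implant status stopped counting, but the eight-year condition stayed. With 20% remote and unconfirmed, 155 × 0.20 × 0.90 = 27.9 event-free subjects would drop out while all 155 × 0.10 = 15.5 events stayed. As a simple proportion, survival would be 1 − 15.5 / (155 − 27.9) = 87.8%. That is an error of 2.2 points in the opposite direction, larger than the bias being corrected in any row of the table.

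**The case against.** The strongest reply is that the remote provision is permissive. It says which forms may be completed off site and suspends no other duty. Surgery on the ankle must still be reported, adverse event assessment is scheduled at every post-operative visit, telephone contact is allowed, returned forms are reviewed by the site, and monitoring includes resolving missing or inconsistent data. This stands as far as the duty goes. It supplies no procedure for learning of surgery done elsewhere on a subject the site does not see.

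Four stronger readings are tempting, and the documents do not support them.

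- A reader might infer that remote subjects are asked nothing about the implant. The case report forms are only listed in the protocol appendix, so their items cannot be read, and the satisfaction item does concern the implant. What can be said is that no revision or reoperation enquiry is specified for remote contact.
- A reader might take the SAP to say outright that a posted form makes a subject event-free to that date. This depends on how two undefined terms are read.
- A reader might infer that those who stop attending are the likeliest to have been revised elsewhere. Neither document says so.
- A reader might apply the whole 10-year risk to remote subjects, giving 91.0% for 20% remote and half unreported, and 93.0% for 30% remote and all unreported. That treats them as never seen on site, although revisions before they became remote would have been open to capture at visits.

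**Conclusion.** The gap is real and worth closing. The remote route specifies no revision enquiry, entry to the survivorship analysis rests on an undefined late score, and censoring does not require known implant status. Together these allow an unreported revision to be carried as event-free time in the primary analysis.

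This mechanism acts in one direction, upward. Its size cannot be derived from the documents. Under the stated assumptions it is about 0.1 to 1.5 points at a true survival of 90% with remote follow-up after year 5, and about 0.5 points in the middle case. That is well inside the 4.7-point half-width, but the interval reflects sampling error only and does not cover missed events. The net direction of the 10-year estimate is a separate matter, because the late-score rule on its own pushes survivorship down.

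**What to change.** 1. **Protocol, Study Duration section.** At every remote contact, record whether the implant is in place, any surgery on the study ankle since the last contact (with date and hospital), and vital status. If the existing case report forms already collect this, say so and require them at remote contacts.
2. **SAP, Survivorship section.** Censor event-free subjects at the last date on which implant status was confirmed, not at the last PROM form.
3. **SAP, Report Timing of survivorship assessment.** Remove late follow-up scores as an entry condition at both the 5- and 10-year assessments. Include all implanted subjects, censored as in item 2, so that unconfirmed event-free subjects contribute time up to their last confirmed status and are not dropped while failures are kept.

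Items 2 and 3 must be made together, for the reason shown in the last step of the working. The cost is a few added questions, a small protocol amendment and revised SAP wording. Remote contacts become slightly longer, and some subjects' follow-up time will be shortened.
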